#### **8.4.2. Demographic Data and Baseline Characteristics**

Demographic summaries will include sex, race/ethnicity, randomization stratification group, and age.

Baseline characteristics will include a summary of body weight, height, and body mass index.

Demographic and baseline characteristics will be summarized using standard descriptive methods.

## **8.5. Efficacy Analysis**

### **8.5.1. Primary Analysis**

The null hypothesis is that addition of GS-5745 to mFOLFOX6 will not improve OS in first-line patients with advanced gastric cancer. The alternative hypothesis is that addition of GS-5745 to mFOLFOX6 will improve OS.

The Kaplan-Meier (KM) method and logrank test stratified by ECOG status (0 or 1), geographic region (Latin America or other participating countries), and primary tumor site (gastric or GEJ) will be used to compare the 2 treatment groups. A Cox proportional hazard model with the same stratification factors will be used to estimate the hazard ratio and corresponding 95% confidence interval (CI).

### **8.5.2. Secondary and Exploratory Analyses**

CCI

### **8.5.3. Control of Type I Error Rate in Efficacy Analyses**

In the efficacy analyses, the following procedures will be implemented to preserve the overall type I error rate across the primary and secondary endpoints of the study, and at interim and final analysis, at a 1-sided significance level of 0.025.

The primary endpoint analysis will serve as the gatekeeper for the secondary endpoint analyses, ie, the primary efficacy endpoint must be met before the secondary efficacy endpoints can be tested. The secondary endpoints included in this sequential testing approach are (1) PFS and (2) ORR.

If the primary hypothesis is rejected, the 2 secondary endpoints will be sequentially tested at the 1-sided 0.016 significance level in the order listed above. If a null hypothesis is not rejected, formal sequential testing will be stopped and only nominal significance will be cited for the remaining secondary endpoints. Analyses and p-values will be reported for all the efficacy endpoints, including the primary endpoint, the secondary endpoints, and all of the exploratory endpoints.

## **8.6. Safety Analysis**

All safety data collected on or after the date that GS-5745/placebo was first administered up to the date of last dose of GS-5745/placebo or mFOLFOX6 or 5-FU and LV (whichever is later) plus 55 days will be summarized by treatment group (according to the treatment received). Data for the pre-treatment and post-treatment follow-up period will be included in data listings.

In general, count and percent of subjects will summarize categorical and ordinal data. Mean, standard deviation, minimum, quartiles, median, and maximum will summarize continuous data.

### **8.6.1. Extent of Exposure**

A subject's extent of exposure to GS-5745 will be generated from the study drug administration eCRF page. Exposure data will be summarized by treatment group.

### **8.6.2. Adverse Events**

Clinical and laboratory adverse events will be coded using the Medical Dictionary for Regulatory Activities (MedDRA). System Organ Class (SOC), High-Level Group Term (HLGT), High-Level Term (HLT), Preferred Term (PT), and Lower-Level Term (LLT) will be attached to the clinical database.

Events will be summarized on the basis of the date of onset for the event. A treatment-emergent adverse event is defined as any adverse event with onset date on or after the date of first dose of study drug up to 55 days after permanent study drug discontinuation or any adverse events leading to premature study drug discontinuation.

Summaries (number and percentage of subjects) of treatment-emergent adverse events (by SOC, HLT, and PT) will be provided by treatment group.

### **8.6.3. Laboratory Evaluations**

Selected laboratory data (using conventional units) will be summarized using only observed data. Data and change from baseline at all scheduled time points will be summarized.

Graded laboratory abnormalities will be defined using the NCI CTCAE (version 4.03). Maximum post-baseline grade will be summarized by count and percent of subjects with each grade.

Incidence of treatment-emergent laboratory abnormalities, defined as values that increase at least 1 toxicity grade from baseline at any time post-baseline, will be summarized by treatment group. If baseline data are missing, then any graded abnormality (ie, at least a Grade 1) will be considered treatment-emergent.

Laboratory abnormalities that occur before the first dose of study drug will be included in data listings.

#### **8.6.4. Other Safety Evaluations**

Similar general approaches to the AE and clinical laboratory data will be utilized to summarize other safety measures.

#### **8.7. Pharmacokinetic Analysis**

The plasma concentration data of GS-5745, oxaliplatin, and 5-FU (and metabolite, if applicable) will be summarized by nominal sampling time using descriptive statistics (eg, sample size, arithmetic mean, geometric mean, coefficient of variation (%), standard deviation, median, minimum, and maximum). PK parameters ( $C_{max}$ ,  $T_{max}$ ,  $C_{last}$ ,  $T_{last}$ ,  $C_{tau}$ ,  $\lambda_z$ ,  $AUC_{last}$ ,  $AUC_{tau}$ , and  $t_{1/2}$ , as applicable) will be listed and summarized using descriptive statistics. Plasma concentrations over time may also be plotted in semi-logarithmic and linear formats as mean  $\pm$  standard deviation, and median (Q1, Q3). Exposures ( $C_{max}$  and AUC) of oxaliplatin and 5-FU with or without co-administration of GS-5745 will be compared to evaluate if GS-5745 treatment alters the PK of oxaliplatin/5-FU.

Exposure-response analysis may be explored as appropriate.

The number and percentage of positive or negative anti-GS-5745 antibody values at each specified timepoint will be summarized. The effect of anti-GS-5745 antibody on GS-5745 PK, safety, and efficacy may be evaluated.

#### **8.8. Biomarker Analysis**

##### **8.8.1. Pharmacodynamic and Exploratory Biomarker Analysis Analysis**

CCI

#### **8.9. Patient-Reported Outcomes**

The values and change from baseline for EQ-5D-3L index scores and the visual analog scale (VAS) will be summarized by descriptive statistics by visit for each treatment arm.

The EORTC QLQ-C30 and QLQ-STO22 questionnaire will be scored according to EORTC guidelines, such that all scales from 0 to 100, with higher functioning and global scores representing better QoL and higher symptom scores representing greater symptom burden. The values and change from baseline for QLQ-C30 and QLQ-STO22 scores will be summarized by descriptive statistics by visit for each treatment arm.

The time to QLQ-C30 and QLQ-STO22 deterioration is defined as the time from randomization to the first deterioration of  $\geq 10$  points from baseline. If no deterioration was observed, censoring occurs at the date of the last assessment. The hazard ratio and the 95% CI comparing the treatment and placebo arm will be provided using the Cox proportional hazard model.

The QLQ-C30 and QLQ-STO22 analysis will also characterize each post baseline assessment as Improved if the improvement from baseline is  $\geq 10$  points, and Stable if the change from baseline is within +/-10 points, exclusive. The proportion of subjects in each treatment arm with Improved/Stable scores will be summarized at each time point and overall. The odds ratio and the 95% CI comparing the treatment and placebo arm will be provided.

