#### **6.2.10. Patient-reported Outcomes Assessments**

Patient-reported outcomes (PRO) will be collected at Day 1 of each cycle, EOT and EOS visits, and at the 30 day safety follow up visit prior to any assessments in the clinic.

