### **8.4. Data Handling Conventions**

#### **8.4.1. General Methods**

By-subject listings will be created for important variables from each eCRF module.

Summary tables for continuous variables will contain the following statistics:

N (number in analysis set), n (number with data), mean, standard deviation (std), 95% confidence intervals (CIs) on the mean, median, minimum, and maximum. Summary tables for categorical variables will include: N, n, percentage, and 95% CIs on the percentage. Unless otherwise indicated, 95% CIs for binary variables will be calculated using the binomial distribution (exact method) and will be 2-sided. Data will be described and summarized by relevant treatment arm, analysis set, and time point. As appropriate, changes from baseline to

each subsequent time point will be described and summarized by treatment arm. Similarly, as appropriate, the best change from baseline during the study will also be described and summarized by treatment arm. Graphical techniques (eg, waterfall plots, Kaplan-Meier curves, etc.) may be used when such methods are appropriate and informative.

The baseline value used in each analysis will be the last (most recent) pre-treatment value.

Subjects with discrepancies between the stratification factor values at randomization and the actual values as documented on data review will be categorized in the analyses according to the actual values. In the situation that there is insufficient information in a stratum (ie, if there are < 6 subjects or there are no events in a stratum), that stratum will be pooled with the smallest adjacent stratum for stratified analyses; the smallest stratum is defined as that stratum having the fewest number of subjects or the fewest number of events in case the former is a tie and the adjacent stratum is defined as a stratum having 2 factors of the 3 at the same level. Data from all sites will be pooled for all analyses. Analyses will be based upon the observed data unless methods for handling missing data are specified. If there is a significant degree of non-normality, analyses may be performed on log-transformed data or nonparametric tests may be applied, as appropriate.

Unless otherwise specified, all analyses will be 1-sided at the 0.025 level of significance.

The following censoring conventions will be applied to tumor control endpoints:

- OS: Data from surviving subjects will be censored at the last time that the subject was known to be alive.

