## **3.3. Strata and Covariates**

Subjects will be randomly assigned to treatment groups via the interactive web response system (IWRS) in a 1:1 ratio using a stratified randomization schedule. Stratification will be based on the following variables:

- Geographic regions: Latin America vs All Other Countries
- ECOG status: 0 vs 1
- Tumor site: Gastric vs GEJ

If there are discrepancies in stratification factor values between the IWRS and the clinical database, the baseline values recorded in the clinical database will be used for analyses.

Efficacy endpoints will be evaluated using stratification factors as covariates or stratification variables for analyses, as specified in Section 6.

In the situation where there is insufficient information in a stratum (ie, if there are < 6 subjects or there is no informative event in a stratum by combined treatment arms), pooling of the stratum may be considered with the smallest adjacent stratum for stratified analyses; the smallest stratum is defined as that stratum having the fewest number of subjects or the fewest number of events in case the former is a tie and the adjacent stratum is defined as a stratum having 2 factors of the 3 at the same level and the other factor at an adjacent level.

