### 6.2.3.2. Objective Response Rate

The ORR will be compared between the 2 treatment arms using the Cochran-Mantel-Haenszel test adjusted for the stratification factors based on the ITT analysis set. ORR and the corresponding 95% CI based on Clopper-Pearson method of each treatment arm will be presented. The odds ratio comparing the 2 treatment arms adjusted for the stratification factors will be presented along with 95% CI. The 2-sided 95% CI of difference for ORR between the treatment and placebo will be calculated based on stratum-adjusted CMH proportion {Koch 1989}.

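### Protocol 8.9 states the PRO deterioration hazard ratio and the Improved/Stable odds ratio without the baseline score; include it as a covariate in both models

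*Protocol*

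**What the plan says.** Protocol 8.9 sets out two PRO comparisons. Time to deterioration is "defined as the time from randomization to the first deterioration of" at least 10 points from baseline, and then: "The hazard ratio and the 95% CI comparing the treatment and placebo arm will be provided using the Cox proportional hazard model". Each post-baseline score is also classed as Improved or Stable against the same 10-point limit, and for that proportion: "The odds ratio and the 95% CI comparing the treatment and placebo arm will be provided". The first sentence names a model but no covariates or strata. The second names no model.

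The baseline score exists. Protocol 6.2.10 says "Patient-reported outcomes (PRO) will be collected at Day 1 of each cycle", and Protocol Appendix 2 marks both EORTC questionnaires at Cycle 1 Day 1.

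Other endpoints are treated differently. For OS, Protocol 8.5.1 says "A Cox proportional hazard model with the same stratification factors will be used to estimate the hazard ratio". SAP 6.2.3.1 adjusts the PFS Cox model for the same factors, and SAP 6.2.3.2 says of ORR: "The odds ratio comparing the 2 treatment arms adjusted for the stratification factors will be presented along with 95% CI".

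SAP 3.3 gives a general rule: "Efficacy endpoints will be evaluated using stratification factors as covariates or stratification variables for analyses, as specified in Section 6". The exploratory part of that section, SAP 6.3, is redacted.

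Protocol 8.5.3 places only PFS and ORR after OS in the testing sequence, but says that p-values will be reported for the exploratory endpoints too. No PRO effect size or power is stated anywhere that can be read.

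**The concern.** Both outcomes are defined by how far a subject moves from his or her own starting score, so the starting score should predict them. A score that is high by chance at baseline tends to fall back, and one that is low tends to rise.

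The scales are also bounded. On a functional scale, a subject below 10 cannot lose 10 points and one above 90 cannot gain 10. By the scoring rules in SAP Appendix 5, a single-item scale with range 3 can take only the values 0, 33.3, 66.7 and 100. A subject at the worst level of such a scale can never have the deterioration event, and one at the best level can never be Improved.

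Leaving out a strongly prognostic covariate moves a hazard ratio or odds ratio toward 1 and makes its test less sensitive. At stake are the size of the reported PRO effect and its nominal p-value.

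**Working it through.** **The plan's own figure.** There is none for the PROs. The nearest powered figure is the 286 OS events in Protocol 8.11 (HR 0.70, 85% power, 1-sided 0.025). It reproduces and is not in question:

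- Schoenfeld: 4 x (1.960 + 1.036)^2 / (ln 0.70)^2 = 35.91 / 0.1272 = 282.3, so 283 events. Freedman's formula gives 289.
- Group-sequential check with the stated boundaries (Z 2.509 at 191 events, 1.993 at 286): overall 1-sided alpha 0.0250, power 0.850.

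**Inputs for the PRO check.** From the documents: 430 subjects, 1:1 within eight strata (three binary factors), 1-sided 0.025. Everything else is assumed:

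- factor prevalences 60%, 15% and 30%;
- deterioration hazard 0.10 per month in the reference group, censoring hazard 0.08 per month, 24-month cap (about 215 to 250 events);
- conditional HR 0.70 or conditional OR 1.75;
- a standardized baseline score with the log-effect per SD shown below;
- modest effects of the randomization factors, set to zero in the rows marked 0.

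There were 1,000 simulated trials per row. The Monte Carlo standard error of one power figure near 70% is sqrt(0.7 x 0.3 / 1000), about 1.4 points. The three analyses in a row use the same simulated trials.

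**Power (%), Cox model**

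| Baseline log-HR per SD | Unadjusted | Stratified | Stratified + baseline | Change |
|---|---|---|---|---|
| 0 | 73.6 | 72.5 | 72.1 | -1.5 |
| 0.2 | 70.9 | 69.1 | 71.3 | +0.4 |
| 0.4 | 72.6 | 71.2 | 76.3 | +3.7 |
| 0.7 | 62.2 | 61.4 | 76.6 | +14.4 |

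**Power (%), logistic model**

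| Baseline log-OR per SD | Unadjusted | Factors | Factors + baseline | Change |
|---|---|---|---|---|
| 0 | 78.6 | 78.7 | 78.7 | +0.1 |
| 0.3 | 77.0 | 77.2 | 78.8 | +1.8 |
| 0.6 | 73.4 | 74.2 | 77.2 | +3.8 |
| 1.0 | 63.5 | 64.3 | 72.0 | +8.5 |

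Under no treatment effect, rejection was about 2 to 3% in every analysis.

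**Where the gain comes from.** In the strongest rows the standard error does not shrink. The estimate moves away from 1 by more than the standard error grows:

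- HR: 0.747 (SE 0.128) unadjusted, |ln HR|/SE = 0.292/0.128 = 2.28. Adjusted: 0.701 (SE 0.133), 0.355/0.133 = 2.67.
- OR: 1.58 (SE 0.199) unadjusted, ln OR/SE = 0.458/0.199 = 2.30. Adjusted: 1.77 (SE 0.223), 0.572/0.223 = 2.56.

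**Check on the score scale.** A second simulation generated 4-weekly scores and applied the 10-point rule. Assumptions: SD 20, within-subject correlation 0.5/0.6/0.7, ECOG shift of 8 points at baseline and 12 on study, 5-point arm effect, PFS medians 9 and 12.9 months, 400 runs, Monte Carlo standard error about 2.5 points. Adding baseline score and ECOG raised power for the hazard ratio from 61/70/88% to 73/80/90%, and for the Week 24 odds ratio from 41/43/59% to 45/48/62%. At correlation 0.6 the HR was 0.75 unadjusted and 0.72 adjusted. The gain at correlation 0.7 for the HR (2 points) is within simulation error.

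**The case against.** **The governing text may be hidden.** SAP 6.3 is redacted, SAP 3.3 sends the reader to Section 6, and SAP Appendix 5 reproduces the EORTC scoring, so a PRO analysis section probably exists. A short protocol sentence is also weak evidence of an unadjusted model: the synopsis describes the OS Cox model without its factors, and Protocol 8.5.1 then supplies them. This stands. A reader might infer that the whole plan omits adjustment; the documents do not support that. What can be said is that the readable rule in Protocol 8.9 does not include the baseline score.

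**The unadjusted ratio is legitimate.** A reader might infer that it is biased, or that power is given away for nothing in return. Neither follows. Hazard and odds ratios are non-collapsible: the unadjusted value is a valid marginal effect and the adjusted one is conditional. Choosing between them is a choice of estimand.

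**The gain is uncertain.** Every prognostic strength above is assumed, and with an uninformative baseline there is no gain. This also stands, but the loss in that case is at most about 2 points.

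**Denominators are a different question.** Under "Analyses will be based upon the observed data unless methods for handling missing data are specified" in Protocol 8.4.1, the by-visit odds ratios cover only subjects still assessed, and a reader might want everyone with a baseline score counted. With PFS median 9 months and HR 0.70 (Protocol 8.11), retention at Week 48 (11.04 months) is exp(-ln 2 x 11.04/9) = 0.427, against 0.427^0.7 = 0.551. If 70% of those assessed are Improved/Stable in both arms (assumed), the observed-data OR is 1.00. Counting all subjects gives 29.9% against 38.6%, an OR of 1.47. That shift comes entirely from PFS, so it is a contestable change of estimand and not the repair of an error.

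**Conclusion.** The point holds for the text of Protocol 8.9. Two outcomes defined as 10-point changes from baseline are compared without the baseline score, which is collected, and including it is the better analysis.

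Nearly all the benefit comes from the baseline score. Adding the randomization factors by themselves changed power by about -2 to +1 point; the reason to include them is consistency with OS, PFS and ORR. Together, the change is about -2 to +14 points for the hazard ratio and 0 to +9 for the odds ratio. It is material only if baseline is at least moderately prognostic, which the 10-point definition and the scale limits make plausible but the documents do not quantify.

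The consequence is limited. The PROs are not among the listed secondary endpoints and carry no alpha and no planned power. Exploratory estimates and nominal p-values are affected; the OS, PFS and ORR conclusions are not.

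**What to change.** In Protocol 8.9:

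- Fit the time-to-deterioration Cox model with the baseline score of the scale concerned as a covariate, stratified by ECOG status, region and primary tumor site.
- Estimate the Improved/Stable odds ratio by logistic regression with the baseline score and the same three factors, and name that model.
- Say that these are conditional effects, and keep the unadjusted hazard ratio and odds ratio as supportive marginal estimates.
- Confirm that the redacted SAP 6.3 says the same, and align it if it does not.

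The cost is a few sentences and a few lines of code. No new data are needed. No subject is lost through the covariate, because neither outcome can be derived without a baseline score. The existing pooling rule for sparse strata in SAP 3.3 can be applied unchanged.

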### 8.10. Interim Analyses

Two formal interim analyses (detailed in [Appendix 6](#)) are planned: the futility interim will be performed at approximately 33.3% information and the efficacy interim at 66.7% information. The final analysis will occur when 286 OS events have been observed.

The Lan-DeMets approach with O'Brien-Fleming type alpha spending function will be used to control the type I error rate for testing. The stopping boundaries at each efficacy analysis time are provided in [Table 8-1](#).

**Table 8-1. Stopping Boundaries for Efficacy Analyses**

Efficacy Analysis	Events (%)	Stopping Boundary	
		Z scale	One-sided p-value scale
Interim	191 (66.7%)	2.509	0.006
Final	286 (100%)	1.993	0.023

Given significance of OS at either the interim or final analysis, the secondary endpoints of PFS and ORR will sequentially tested at the 1-sided 0.016 significance level.

If the DMC sees substantial evidence of benefit of the GS-5745 + mFOLFOX6 combination, (ie, OS is significantly better in Arm A compared to Arm B), Gilead personnel who are not involved with the study may perform an unblinded review of the integrated interim data, and may decide to stop the study and offer GS-5745 treatment to those subjects who are still enrolled in Arm B.

### 8.11. Sample Size

Assuming a median OS time for the mFOLFOX6 + placebo group of 11.5 months, 286 events are needed to detect a hazard ratio (HR) of 0.70 with 85% power at a 1-sided significance level of 0.025 using a log-rank test, given 1 efficacy interim at 66.7% information. With an accrual period of 18 months, minimum follow-up of 18 months, and a 10% annual dropout rate, a total sample size of 430 subjects (215 subjects per treatment group) is needed to observe the required 286 events within the given time frame.

As the targeted number of deaths is large (~286), if the null hypothesis of the primary end point of OS is rejected, it will convincingly demonstrate clinical treatment effect and would provide a narrow confidence interval. Based on the number of deaths and the assumed treatment effect on OS in the protocol, the expected 95% confidence interval on HR of OS between the 2 treatment groups is approximately (0.627, 0.996). At the time of final analysis and assuming OS is significant, PFS will be tested at one-sided type I error of 0.016. Assuming that the hazard ratio for PFS is 0.7, which is expected to be on par or better than the treatment effect in OS, and that median PFS for the control is 9 months, a sample size of 430 subjects (322 PFS events) will provide 85% power under the planned study enrollment (18 months), follow-up duration (18 month), and drop-out rate (annually 10%).

